During remote visits, adverse event recording will be recorded by the site. If the subject has agreed to the use of the Engage application on their phone, the subject will also complete a pain assessment for each burned area (Burn A and Burn B). For the Engage application, the subject number will be obtained for registration and completion of the e-diary. The subject will set up a personal identification number (PIN) and provide responses to security questions that will be used if they forget their PIN. The e-diaries will be completed via a web application on the mobile phone that is hosted in a database. As a Software-as-a-Service (SaaS) provider of clinical trial software and services, Clinical Ink acts as an agent on behalf of customers to collect Clinical Study Data. With respect to all Clinical Study Data, the collecting and processing of data are governed by the contractual relationship with each customer consistent with the notice provisions specified by the customer in their relationship with the individuals participating in the clinical study.

If the subject agrees to and is able, the subject will capture photographs of the wounds and upload to the MyChart application. Briefly, the subject will obtain the photograph and navigate to the MyChart application utilizing the web-browser on their phone. The subject should then navigate to the “Messaging” center and click “Ask a Question”. From here, the subject selects “New Medical Question.” The subject should choose their study physician and mark a “Visit Follow-Up Question”. They then can attach an image and click send.

During office visits on days 14 and 28, adverse event recording, incidence of infection, assessment of reepithelialization, photography, and a pain assessment will be completed for each burned area (Burn A and Burn B). A \$45 gas card (one per visit) and KeraStat Gel-related dressing supplies will be given to the subject during these visits, as well.

Partial thickness burns that do not require excision and grafting are expected to be fully closed within 21 days. Thus, after assessment at discharge, subjects will be followed bi-weekly until 4 weeks post-burn to ensure appropriate healing. Then, subjects will be seen at 3 months (± 7 days), 6 months (± 7 days), and 1 year (± 14 days) post-enrollment for site photographs and in order to assess the development of scarring using the Patient and Observer Scar Assessment Scale (POSAS), and TEWL measurements.

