Dressings will be changed per institutional SOC guidelines but at a minimum of every 3 days. Subjects will return to the clinic on days 14 ± 3 and 28 ± 3 post-enrollment for the first 4 weeks and at months 3 (± 7 days), 6 (± 7 days), and 12 (± 14 days) post-enrollment. Subjects will also participate in a remote visit on days 7 ± 3 and 21 ± 3 post-enrollment. Dressing changes will be continued until reepithelialization is achieved. During each visit, study staff will document the number of dressing changes that occurred outside of clinic visits as well as any pertinent information related to the dressing changes. During visits when dressing changes are still necessary, subjects will complete the VAS pain score before and after dressing changes to each burn, and any unanticipated adverse events related to the device will be logged. Subjects who are able and willing will download an application on their smartphone that will prompt them to record the VAS pain score before and after dressing changes will complete this during remote visits on days 7 and 14. Subjects will also be asked to upload photos of the burns at days 7 and 21 utilizing the medical center's MyChart application. Appearance of the sites will be assessed at months 3, 6, and 12 using the POSAS. During the visits at 3, 6, and 12 months, sites will be subjected to 3 measurements of TEWL. Photographs will be obtained at all in-person visits and may be subjected to wound closure and percent epithelialization measurements via ImageJ. Recording of adverse events (AE), measurement of vital signs, examination of the wound/site of wound, and notation of concomitant medication and procedures will also take place during each visit. All measures will be completed if an individual agrees to a final visit after withdrawal from the study.

Masking

This study will be an open-label study.

Schedule of Events

Baseline Testing (All subjects)

- Photographs (prior to start of treatment)
- Vital signs (e.g., blood pressure, heart rate, temperature, height, weight)
- Examination of wound, including wound measurement
- Concomitant medications
- VAS pain score before and after dressing application

Discharge

- Adverse events

- Vital signs
- Examination of wound, including wound measurement and percent reepithelialization
- Photography of treatment site
- Concomitant medications and procedures
- Dressing change
- VAS pain score before and after dressing change

Day 7, 21 (± 3 , Remote visit)

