- Photography of treatment site on days 7 and 21 (optional)
- VAS pain score before and after dressing changes (optional)
- Adverse events

Day 14, 28 (± 3) Evaluation

- Adverse events
- Vital signs
- Examination of wound, including wound measurement and percent reepithelialization
- Photography of treatment site
- Concomitant medications and procedures
- Documentation of number and description of dressing changes since last visit (for subjects who do not participate in the optional tracking)
- Dressing change
- VAS pain score before and after dressing change

3 Month (± 7 days), 6 Month (± 7 days), 1 Year (± 14 days) Evaluation

- Adverse events
- Vital signs
- Examination of wound/site of wound, including wound measurement
- Photography of treatment site
- Concomitant medications and procedures
- POSAS
- TEWL

Early Termination Visit/Withdrawal from Study

- Adverse events
- Vital signs
- Examination of wound, including wound measurement
- Photography of treatment site
- Concomitant medications and procedures

- Dressing change (Month 1)
- VAS pain score before and after dressing change (Month 1)
- POSAS (Months 3-12)
- TEWL (Months 3-12)

Outcome Measure(s)

Assessments	Screening/Day 0	Discharge	Remote Follow-Up (Days 7 ±3 and 21 ±3)	First Month Follow-Up (Days 14 ±3, 28 ±3)	3 Month (±7 day), 6 Month (±7 day), 1 Year (±14 day) Follow-ups	Early Termination Visit
Written Informed Consent	X					
Demographic and Medical History	X					
Inclusion/Exclusion Criteria	X					
Randomization*	X					
Unanticipated Adverse Device Events		X	X	X		X
Adverse Events		X	X	X	X	X
Vital Signs	X	X		X	X	X
Examine Wound/ Site of Wound, including wound measurement	X	X		X	X	X
Photography of Treatment Sites	X	X	X**	X	X	X
Concomitant Medications	X	X		X	X	X
Concomitant Procedures		X		X	X	X
Dressing Changes	As needed	As needed	As needed	As needed		
VAS Pain Score	X	X	X**	X		X
Wound Closure (Investigator assessment)				X		X
Percent epithelialization				X		X

Assessments	Screening/Day 0	Discharge	Remote Follow-Up (Days 7 ±3 and 21 ±3)	First Month Follow-Up (Days 14 ±3, 28 ±3)	3 Month (±7 day), 6 Month (±7 day), 1 Year (±14 day) Follow-ups	Early Termination Visit
(Investigator assessment)						
Cosmesis of Treatment Sites (POSAS)					X	X
TEWL					X	

*Randomization will occur after confirmation of inclusion and exclusion criteria.

**These activities will be optional and dependent on whether subject has resources for use of an at-home application.

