Photographs will be obtained during each subject contact. Photos will be obtained from a distance of approximately 18 inches (if possible) so as to encompass each burn in its entirety. A ruler will lay flush with adjacent uninjured skin and will be included in each picture. Cameras and downloading capabilities should be tested prior to enrolling the first subject. Only jpeg images taken with a digital camera will be accepted. Photographs are a requirement of participation in this clinical trial. Optional photographs will be collected on days 7 and 21 by subjects who are able and willing to upload photos utilizing the institution's MyChart application.

Additional points:

Baseline photographs must be taken after informed consent but prior to randomization.

Images will be transferred from the site's camera to the patient portal. The file naming convention is Patient Acrostic_Burn ID_Visit Number.

At the visit where complete wound closure is documented, the photographs of the burns may be subjected to analysis using ImageJ to confirm wound closure.

Study Subject Withdrawal

Subjects may withdraw from study participation at any time. Decision to withdraw should be noted on the CRF including the date and reason. Study staff should ask subject if he/she will agree to a final visit, and this should be noted on the CRF as well.

Analytical Plan

Descriptive statistics for continuous variables and frequency counts and percentages for categorical demographics variables will be summarized by subject and by burn treatment group. Listings will be created for all data by Case Report Form. A Statistical Analysis Plan (SAP) that includes mock tables, listings and figures (TLFs) will be developed and finalized prior to the lock of the clinical database. The extent to which missing data occurs will be described with an interpretation of the extent on the impact of the analysis as well as generalizability of the data.

Statistical analyses will be conducted for two analysis populations.

- a. Intention to treat: All subjects randomized will be included in the analyses.
- b. Safety: All subjects that have received one or more treatment applications will be included in the safety analysis for all safety endpoints.

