For the primary objective of the study, improved cosmesis will be analyzed using data from the POSAS, as a total score, and separately for the observer score and then the subject score. Changes from baseline will be examined at 3 months, 6 months and again at 1 year post treatment. TEWL will be considered at 3 months, 6 months, and 1 year. This analysis may also consider the baseline status of the burn including depth, surface area, location of the burn injury and subject baseline characteristics (age, concomitant injury).

Protocol version: 5

Template updated 5 Jul 2021

Secondary objectives include determining whether KeraStat Gel wound dressing results in less painful dressing changes, faster reepithelialization, and reduction in need for excision and grafting. Improvement in pain will be assessed using the scoring from the VAS pain scale at Screening, Days 7, 14, 21 and 28. Box plots of the VAS pain scores will be presented displaying the medians and quartiles in each treatment group over time. A nonparametric test will be used to determine changes in the score across time (Kruskal-Wallis) as well. Reductions in excision and grafting will be analyzed by treatment groups using the same methods as the VAS pain score. Median time to 100% reepithelialization by study treatment group will be conducted, mean times (days) will be analyzed using a Wilcoxon test by treatment groups, as well as a time to event analysis for 90% or higher reepithelialization from baseline.

The incidence of adverse events will be reported and summarized by treatment group. Adverse events will be coded in MedDRA by system organ class and preferred terms (PT).

Human Subjects Protection

Subject Recruitment Methods

Subjects who present at the Burn Center at WF or UMC with qualifying burns as determined by the Investigator will be approached for inclusion in the study by study personnel.

Remuneration

Enrolled study subjects will be provided with one \$45 gas card per visit for office visits on days 14 and 28 and months 3, 6, and 12.

Informed Consent

All subjects must give their informed consent in accordance with the informed consent regulations in Title 21 CFR, Part 50. Each subject over 18 years and subjects under 18 and their legally authorized representative will execute written informed consent (and assent if applicable) before any study procedures are conducted. Study personnel will obtain written informed consent in the clinic.

Confidentiality and Privacy

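### Time to 100% reepithelialization: the Wilcoxon test is not stated to be paired, and closure is known mainly to a two-week visit interval, so the SAP should specify a within-subject test on that interval

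*Combined protocol and SAP*

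**What the plan says.** The Design section describes a randomized within-subject trial, with one study burn per dressing on every subject. The Sample Size paragraph gives 30 subjects and 60 wounds.

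For the secondary objective of faster healing, the Analytical Plan says: "Median time to 100% reepithelialization by study treatment group will be conducted, mean times (days) will be analyzed using a Wilcoxon test by treatment groups". It adds a time-to-event analysis for reaching 90% or more. Neither analysis is described as paired. No rule is given for deriving a closure day, or for burns that are open, grafted or unassessed.

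The information on when a burn closed is as follows.
- In the Outcome Measure(s) table, the row "Wound Closure (Investigator assessment" and the percent-epithelialization row are marked only at days 14 ± 3 and 28 ± 3 and at early termination.
- The Discharge list under Schedule of Events also includes "Examination of wound, including wound measurement and percent reepithelialization". The table does not mark this at discharge.
- On follow-up, Design says: "Thus, after assessment at discharge, subjects will be followed bi-weekly until 4 weeks post-burn to ensure appropriate healing".
- The photography notes tie closure to a visit: "At the visit where complete wound closure is documented".
- Partial dating information exists. The remote-visit list has "Photography of treatment site on days 7 and 21 (optional", and under Interactions "study staff will document the number of dressing changes that occurred outside of clinic visits". Neither is turned into a closure date.
- On expected healing, Design says: "Partial thickness burns that do not require excision and grafting are expected to be fully closed within 21 days".

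**The concern.** Two features of the trial are missing from the planned comparison.

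First, the burns are paired. The name Wilcoxon covers both the signed-rank test for pairs and the rank-sum test for independent groups, and the plan compares by treatment group without saying which. The same section names Kruskal-Wallis, a test for independent samples, for pain scores across time. An unpaired reading is therefore a live one. It would give up much of what the within-subject design buys, in a trial of only 30 pairs.

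Second, the day scale is largely an artefact of the schedule. A burn that closes on day 15 and one that closes on day 25 would usually both be recorded at the day-28 visit. If most burns close within 21 days, they close before the first scheduled assessment or between the two. A median or mean built from visit days can then jump by a whole visit interval, or show nothing, when the true difference is a couple of days.

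**Working it through.** **No figure to reproduce.** The documents give 30 pairs and the visit days. They give no healing-time distribution, within-subject correlation, effect size or power. Everything below on power is illustrative.

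**Visit spacing (document values).** Nominal gap: 28 − 14 = 14 days. With the windows, the shortest is (28 − 3) − (14 + 3) = 8 days and the longest is (28 + 3) − (14 − 3) = 20 days.

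**Assumptions.** Lognormal healing times; correlation 0.5 between a subject's two burns on the log scale; 30 pairs; two-sided 0.05. Visits vary uniformly within ±3 days and are shared by both burns. In the visit-day analyses, a burn open at day 28 takes its month-3 visit date (91 ± 7). The share beyond day 21 is 1 − Φ(ln(21/median)/log-SD). For median 14 and log-SD 0.25 this is 1 − Φ(0.405/0.25) = 1 − Φ(1.62) = 5%.

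**Power by simulation (slower v faster dressing):**

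| Medians, log-SD | Beyond day 21 | A: unpaired, visit days | B: paired, visit days | C: paired, closure interval | B − A | C − B |
|---|---|---|---|---|---|---|
| 14 v 12, 0.25 | 5% v 1% | 0.31 | 0.46 | 0.52 | 0.15 | 0.06 |
| 14 v 12, 0.35 | 12% v 5.5% | 0.17 | 0.30 | 0.34 | 0.13 | 0.04 |
| 17 v 14, 0.35 | 27% v 12% | 0.30 | 0.48 | 0.56 | 0.18 | 0.08 |

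Repeat runs of the same model agree to within about 0.03. One gave 0.32, 0.17 and 0.29 for A and 0.53, 0.35 and 0.54 for C. The first row is closest to the protocol's 21-day expectation; the third is slower than it expects.

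**Why the unpaired test is conservative.** With correlation ρ, the variance of the mean difference is proportional to 2(1 − ρ), but an unpaired test uses 2. At ρ = 0.5 the statistic shrinks by √0.5 = 0.71, so the cut-off of 1.96 acts like 1.96/0.71 ≈ 2.77, a two-sided level of about 0.006. On exact days, simulation gives 0.007 for rank-sum. On the visit grid, null rejection is about 0.01 unpaired and 0.04 to 0.05 paired.

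**Sensitivity to correlation** (14 v 12, log-SD 0.35; C, B, A): ρ = 0: 0.26, 0.22, 0.21. ρ = 0.3: 0.30, 0.28, 0.21. ρ = 0.7: 0.43, 0.40, 0.15. Pairing costs nothing at zero correlation.

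**Medians in visit days.** For a dressing with true median 14, about half the burns are closed by day 14, so the recorded median falls near day 14 or near day 28 almost by chance. With true medians 14 v 12, recorded medians differ by 10 days or more in 27 to 33% of trials and by 1 day or less in 29 to 35%.

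**Open burns.** The share still open after the day-28 visit is 0.4% v 0.1%, 2.6% v 0.9% and 8.1% v 2.6% in the three scenarios. Dropping open pairs moves B from 0.46 to 0.45, 0.30 to 0.27 and 0.48 to 0.37.

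**Grafted burns** (independent grafting assumed; 14 v 12, log-SD 0.35; ranked worst v pairs set apart). Grafting 10% in each arm: 0.16 v 0.28. 15% in the slower arm and 5% in the faster: 0.49 v 0.27. The reverse: 0.05 v 0.28. Neither rule dominates.

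**The case against.** The strongest reply is that this is detail deferred, not a wrong analysis. The Analytical Plan promises a SAP with mock tables before database lock, and signed-rank is the natural meaning of Wilcoxon in a within-subject trial. That stands in part. A reader might infer that the plan specifies an unpaired test; it does not. But the promised SAP is not in the text supplied, and in an open-label study the choice is better fixed early.

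A reader might also infer that an unpaired test would inflate false positives. The opposite holds: it is conservative.

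Nor does the plan say that open burns are dropped, or leave late closure unobservable. Wounds are examined at month 3, and under the 21-day expectation almost none would be open at day 28. The open-burn point is therefore minor.

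Finally, the closure interval is partly a preference. It gains little over paired visit days and gives up results in days. Tied pairs carry no weight in a signed-rank test, and only about 10 to 12 of 30 pairs differ in category. A mid-p sign test does about as well (0.53, 0.33, 0.56). Hence equivalent paired methods are acceptable. All power figures rest on assumed healing times, so they illustrate the loss and do not measure it for this trial.

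**Conclusion.** The point holds as under-specification with a concrete better method available, for a secondary objective. Under the stated assumptions, moving from an unpaired test on visit days to a paired test on the closure interval raises power by 0.53 − 0.32 = 0.21, 0.35 − 0.17 = 0.18 and 0.54 − 0.29 = 0.25. Pairing accounts for 0.13 to 0.18 of this, and that part is lost only if the sponsor takes the unpaired reading. The misleading medians do not depend on that reading: they follow from the visit spacing under any test. The size depends on the assumed correlation; at zero correlation the pairing gain disappears. The point should be settled before lock. It does not touch the primary cosmesis objective.

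**What to change.** In the SAP, before database lock:
- Make the 100% comparison a within-subject Wilcoxon signed-rank test on the closure interval: closed by the day-14 visit, closed by the day-28 visit, or not closed by day 28, with open burns ranked last. A sign test or a paired interval-censored model is an acceptable equivalent.
- Report the proportion closed by each visit for each dressing. Label any median as a visit day.
- Account for the pairing in the 90% time-to-event analysis.
- Name one primary analysis rule for grafted burns, with the other as a sensitivity analysis.
- Give a rule for burns unassessed because of withdrawal or a missed visit.
- Reconcile the Discharge list with the schedule table on whether discharge is a reepithelialization assessment.

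The cost is SAP wording and modest programming, with no new data. The downside is that results are stated as closure intervals, not days.

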AEs that are anticipated for this subject population include: neurological/psychological, cardiovascular, pulmonary, gastrointestinal, genitourinary, renal, musculoskeletal, blood, endocrine, skin/wound, infectious, eye/ear/nose/throat, chemical, and hematological complications.

While these events may be temporally associated with study participation, they are consistent with severe burns and may not be considered related to the study under most circumstances. An Investigator (to include other qualified study staff) will be responsible for evaluating individual

subjects and determining whether a specific event is potentially study-related or whether the event could be reasonably anticipated as normal sequelae of the subject's clinical status, injury, and hospital course.

In the event of an AE, the Investigator will use accepted institutional SOC guidelines (medical or surgical), as needed. Expected or unexpected AE will be managed according to institutional SOC guidelines.

All subjects will be treated to alleviate signs and symptoms as appropriate medical intervention dictates. All procedures or medical therapies related to treatment of the complication will be recorded. Investigator assessment of reasons for failure and medical/surgical management will be recorded in the CRF. Subjects who are discontinued from study treatment will remain in the study for safety assessments and efficacy analysis.

All AE will be recorded on the CRF. The time of the onset, location, duration, intensity, relationship to the test product, treatment, and follow-up will also be captured on the CRF. The relationship between the application of KeraStat Gel and the AE will be determined by the Investigator as 'not related' or 'related'. Events other than 'not related' will be considered related in the clinical study report.

Not related: The event is most likely produced by other factors such as the subject's clinical condition, intercurrent illness, or concomitant medications or procedures and does not follow a known response pattern to the study device, or the temporal relationship of the event to study device administration makes a causal relationship unlikely.

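### Time to 100% reepithelialization is analysed as raw days, which leaves no place for a burn that is still open at day 28 or is grafted

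*Combined protocol and SAP*

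**What the plan says.** The Analytical Plan of the combined protocol and SAP has three analyses of reepithelialization: a median time to 100% by group, then "mean times (days) will be analyzed using a Wilcoxon test by treatment groups", and lastly "as well as a time to event analysis for 90% or higher reepithelialization from baseline". So the only method named that can carry an unclosed burn applies to the 90% threshold. No estimator is named for the median, and no paired or censored form for the Wilcoxon test.

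On who is analysed, the same section says "Intention to treat: All subjects randomized will be included in the analyses". The section on reporting unanticipated problems, adverse events and deviations adds "Subjects who are discontinued from study treatment will remain in the study for safety assessments and efficacy analysis".

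On timing, the Interactions section says "Subjects will return to the clinic on days 14 ± 3 and 28 ± 3 post-enrollment for the first 4 weeks"; the next visit is month 3 ± 7 days. The Schedule of Events lists "Examination of wound, including wound measurement and percent reepithelialization" at discharge and at days 14 and 28, but only "Examination of wound/site of wound, including wound measurement" at months 3, 6 and 12. Days 7 and 21 are remote, with optional photographs. The Interactions section also allows ImageJ measurement of closure on photographs from every in-person visit.

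On expected healing, the Design section says "Partial thickness burns that do not require excision and grafting are expected to be fully closed within 21 days". Less excision and grafting is a secondary objective, and failure to close is among the listed risks.

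No section gives a value to a burn that is open at day 28 or grafted. The missing-data sentence promises only a description of extent, and a separate SAP is to be finalised before database lock.

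**The concern.** A mean of days needs a number for each burn. A burn that has not closed, or that was grafted, has no day of closure under the study dressing. The analyst must drop it, assign it a value, or date its closure at the graft. Dropping it sits badly with analysing all randomized subjects, and it removes exactly the burns on which a dressing failed. Dating closure at the graft credits the arm that needed surgery with fast healing.

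Faster reepithelialization is a secondary objective. Both the estimated difference and the chance of detecting it depend on a rule the plan does not state. The study is open-label, so a rule left until shortly before database lock could be set by people who know which dressing had the open burns.

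**Working it through.** The plan gives no closure rate, graft rate, effect size or power for this endpoint, so there is no figure to reproduce. Everything below rests on assumed healing times.

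**Inputs from the documents.** 30 subjects, one burn per dressing each; clinic assessments at days 14 and 28; closure within 21 days expected for ungrafted burns.

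**Assumptions.** Lognormal closure times, within-subject correlation 0.5, closure seen at day 14 or day 28 (discharge assessments and optional photographs ignored), signed-rank test at two-sided 0.05, simulated with 6,000 replicates. Mepilex Ag is taken as the slower arm.

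**Scenario A: healing as the Design section expects.** Medians 15 v 13 days, with 90% of slower-arm burns closed by day 21, so log SD = ln(21/15)/1.2816 = 0.263.
- Share closed at day 14: Φ(ln(14/15)/0.263) = 0.396 v Φ(ln(14/13)/0.263) = 0.611.
- With visit dating, the mean truncated at day 28 differs by 14 × (0.611 − 0.396) = 3.0 days.
- Simulation, no grafts: 0.9% v 0.2% open at day 28; difference 3.04 days if open burns are dropped and 3.03 if set to day 28; power 49% either way. The rule does not matter here.

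**Scenario B: A plus grafts, 3 v 1 of 30 on average, graft at day 14.**
- Grafted burns counted as not closed: shares closed at day 14 are 0.396 × 27/30 = 0.357 and 0.611 × 29/30 = 0.591; difference 14 × 0.234 = 3.3 days (simulated 3.30).
- Graft date counted as closure: 0.357 + 0.100 = 0.457 v 0.591 + 0.033 = 0.624; difference 14 × 0.167 = 2.3 days (simulated 2.38).
- Power: about 50% with grafted burns at the worst rank, about 41% if dropped, about 30% if the graft date counts as closure.

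**Scenario C: slower healing, no grafts.** Medians 18 v 15, log SD 0.35.
- Open at day 28: 1 − Φ(ln(28/18)/0.35) = 0.10 v 1 − Φ(ln(28/15)/0.35) = 0.04, about 3 v 1 burns of 30.
- Power: about 38% if dropped; 50% to 52% with open burns tied at the worst rank, depending on the score used for that rank.
- Dropping is itself ambiguous: removing whole pairs gives a difference of 2.8 days, removing single burns 2.4.

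**Scenario D: A plus equal grafts, 2 v 2 of 30.** Worst rank gives 36% power, against 41% for a mean restricted to 28 days. Here counting grafts as not closed costs power.

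**Error rate.** With equal open shares, the Wilcoxon rules reject in 4.0% to 4.9% of null trials.

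**The case against.** The strongest reply is that this is detail for the SAP. The Analytical Plan is an outline, the SAP is still to be written, and a censored-data form of the Wilcoxon test is not excluded. The plan also has a median, little moved by a few open burns, a time-to-event analysis at 90%, and a separate analysis of grafting. Much of that stands, and it limits the point. It does not close the gap: the 90% analysis has a different threshold and states no graft rule, and raw mean days remain the stated summary for 100%.

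A second reply concerns size. A reader might infer that the reported difference could double or triple. Moving one burn from day 28 to day 90 shifts its group mean by (90 − 28)/30 = 2.1 days, and in some assumed scenarios the difference in means more than doubles. The documents do not support that reading, because no section proposes the month 3 date as an exact closure time. Between dropping burns and setting them to day 28, the simulated differences never part by more than 0.24 day. The cost lies mainly in power and in how grafts count.

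A reader might also infer that closure after day 28 goes unseen. It does not: wound measurement and photographs continue at month 3, and ImageJ closure measurement is allowed there. What is lost is the date, within an interval of 52 days (83 − 31) to 72 days (97 − 25).

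Finally, the obvious remedy of Kaplan-Meier medians has a flaw of its own. Dated by visit, such a median can only be 14 or 28. In Scenario A it shows a 14-day difference in about 76% to 77% of trials, where the true gap in medians is 2 days.

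**Conclusion.** The point holds as a modest one about a secondary endpoint. Raw mean days cannot represent burns that are open at day 28 or grafted, although the plan keeps their subjects in the analysis.

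Under the assumptions above, dropping such burns costs roughly 9 to 14 percentage points of power when they are unequal between dressings (41% v 50% in B; 38% v up to 52% in C). Counting the graft date as closure lowers power to about 30% in B and shrinks the difference from 3.3 to 2.4 days. If nearly all burns close by day 21 without grafts, nothing of note changes. The documents give neither the open share nor the graft share, so which case applies is unknown.

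A reader might go further and conclude that false-positive error is inflated or that the primary result is at risk. Neither follows: the error rate stays near 5% when open shares are equal, and the POSAS analysis does not use these times.

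**What to change.** In the Analytical Plan, for time to 100% reepithelialization:

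- Keep all randomized burns and compare them within subject. Use either a paired signed-rank test with open and grafted burns tied at the worst rank, or an interval-censored (or discrete by visit) time-to-event model that allows for the pairing. Name one as the main analysis. If it is the signed-rank test, state the score for the worst rank (pooled mid-ranks would do), because that test ranks differences and its result depends on the spacing.
- Count a grafted burn as not closed under study dressing. Use neither the graft date nor the month 3 date as an exact closure time.
- In place of raw mean days, report the proportion closed at days 14 and 28 and a mean restricted to 28 days, labelled as such. Do not report Kaplan-Meier medians dated by visit.

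Set this before anyone examines healing data by dressing. Adding closure status at month 3 to the Schedule of Events is optional, since the Interactions section already allows it to be measured from photographs.

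The cost is a few sentences, with no added visit. The downside is a modest loss of power if grafts are equal in both groups: about 36% against 41% for the restricted mean with 2 v 2 grafts of 30.
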